A total of 8-10 community advisory board members (CAB), 42 student nurses from the UNMC Northern Division NRSG 413 Population Centered Care course, and 80 rural male subjects (40 per group) are needed to achieve the proposed objectives. The sample will consist of 80 men (40/group) who meet the inclusion criteria. Hertzog 74suggested that 30 participants per group in a pilot study is a sufficient sample size for aims involving between group differences and if the results are to be used to estimate the needed sample size for a future, fully- powered study. It is important for this study that we obtain reliable estimates of effect size with which to perform a power analysis for subsequent research, so 40 participants per group will be sought, for a total of 80. Some participants will likely not complete the study, so we will enroll 80 men to allow for up to a 30% attrition rate. Power for the repeated measures analysis of variance (RM-ANOVA) was determined using G*Power 3.1.9. A within-between interaction will be the primary test of significance (time*group interaction). Assuming a small effect size ($f=.10$),⁷⁵ a significance level of .05, 3 time points, and an estimate of .5 for the correlation between time points, 164 participants (82 per group) would be needed to have 80% power. Because this is a pilot study, a smaller sample size is justified, and the results of the pilot study will be used to update the power analysis prior to a future study.

Purposeful justification for the total number of community advisory board members and student nurses is based upon their information rich knowledge of the rural context as either community leaders or students in a rural college of nursing. Justification of the total sample size desired for the community advisory board is based upon optimal group function / interaction (8-10 persons) documented in previous advisory board work in agricultural based locales (Kingman, Yoder, Hodge, Ortega, & Field, 2004). Justification for inclusion of 42 student nurses was based upon the aim of the R-15 AREA NIH mechanism to expose undergraduate students to research. Community outreach is a concept taught in NRSG 413- Population Centered Care. It was deemed feasible to involve all students enrolled in this NRSG 413 course to the community outreach activity of this study- without excluding any student.

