Following informed consent and completion of baseline visit, eligible participants will be randomized 1:1 to either intervention or comparison group. Participants randomized to the MT+ group will receive *Lose-It* Premium version (value \$40) and Wi-Fi Nokia Body+ scale (\$100). Participants randomized to the MT group will receive *Lose-It* Basic version (free) plus a \$25 stipend for their participation in each assessment point (3). The men will be randomly assigned to the intervention and comparison groups as they are enrolled using an allocation schedule created by the project statistician. The research nurses will not be blinded to the group assignment as they must conduct the app download on the subject's phone and conduct orientation training of the app with the subject that is specific to their assignment (basic app vs. premium app). Randomization will be predetermined using a random number generator and urn randomization to ensure equal sample sizes.

A comparison group (MT) (n=40) of men will receive the *Lose-It* Basic app. The basic app permits daily self-monitoring of eating and physical activity and manual logging of daily weight. MT participants will be asked at baseline to self-monitor their eating, activity, and weight daily. They will receive no text message prompts for self-monitoring, self-monitoring trend reports, or peer interaction via group. MT participants will complete assessments at baseline, 3 and 6 months postbaseline. MT participants will only receive text message reminders for their assessment visit appointment times.

Description of the Intervention Group (MT+). *Lose-It* Premium permits enhanced customization of goal setting, app automated self-monitoring reminders, customized email reports that outline self-monitoring trends important in supporting motivation and confidence during periods of behavioral action. The Nokia Wi-Fi scale will provide automated coaching, rewards and recording of weight synced to the *Lose-It* app permitting immediate feedback and visual maps of weight trends.

Research Staff Support-Reminder Prompts: MT+ participants will have research staff support available via phone. They will also receive reminder prompts for self-monitoring via text and phone when non-adherence with self-monitoring of dietary intake, physical activity or weight is incomplete for 5 days of greater.

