Analysis: Accelerometers that contain a minimum of five 10-hour days, including both weekday and weekend days, of tracking will be eligible for analysis^{7, 8}. Our collaborating investigators-UNO biomechanical engineer, [name], and Information Science and Technology Specialist, [name], will supervise the advanced analyses of our ActiGraph data with their UNO graduate students across four forms: 1) Traditional ActiGraph analysis (raw accelerations and step counts per 15 second bouts, 2) Custom bout and sedentary analysis, 3) Nonlinear activity pattern analysis, and 4) Applying deep-learning and advanced analytics^{5,9}. Subjects who participate in this sub-study will be mailed a single-page, individualized, easy to read, plain language, graph report containing their peak activity and sedentary times, as well as a report of minutes of minimum, moderate, and vigorous physical activity from their 7-day measurement period. Subjects will be given the same troubleshooting number to call if they have any questions regarding interpreting this individualized physical activity report.

Statistical Analysis

Descriptive statistics will be calculated on all variables, including frequencies and percentages for recruitment/retention, demographic, and categorical variables. Means and standard deviations will be calculated for all continuous variables and measures at each time point. Feasibility and acceptability analyses for aim 1 are largely descriptive, as we will be assessing participation rates and percentages of eligible men and which were the more effective recruitment methods. Qualitative content analysis, as described by Hsieh and Shannon (110) will guide interpretation of the focus group findings from the intervention participant groups. The interview transcript, reflective memos and observation notes taken during each focus group will

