Aim #2: Determine preliminary efficacy of a MT+ intervention to a comparison group receiving only a basic self-monitoring app (MT) in achieving 1) weight loss (primary), and 2) improved diet and increased PA (secondary) at 3 months post-baseline and follow-up at 6 months post-baseline in rural men. The efficacy analyses for aim 2 will be tested via RM-ANOVA models, as they provide a direct measure of differences between the intervention and comparison groups in weight loss and dietary and PA behaviors across the study, as well as effect size estimates. Huynh-Feldt corrected F-tests will be used in order to account for any possible violation of sphericity. If there is a higher than expected attrition rate, a maximum likelihood estimation method (e.g. mixed models) will be used instead of RM-ANOVA in order to utilize all available data and not delete cases in a listwise manner. Overall weight lost at follow-up will be assessed via an independent groups t-test. Outcome variables that are not normally distributed will either be transformed or assessed with nonparametric methods.

Aim #3: Determine quantitative and qualitative indicators of community capacity (resource mobilization, learning opportunities-skills development, partnership linkages, participatory decision- making, leadership) to support a relevant weight loss intervention for rural men. For aim 3, multiple indicators of community capacity will be used to evaluate support for the weight loss intervention applying best practice recommendations (113), 1) CAB- assessed community capacity change survey report by CAB, participation level of members (i.e. # meetings, activities, resources allocated, partnership/network linkages, leadership roles assumed), member attrition with reasons, Qualitative indicators of community capacity in CAB include perceived benefits/skills gained, barriers and facilitators of retention, proposed strategies to increase retention, CAB evaluation of student outreach activities, 2) STUDENTS- clinical log of community outreach activities (type, number, hours) developed, implemented, and outcome,

leadership activities (dissemination via honors projects, clinical conference and class presentations). Qualitative indicators of community capacity among students will include perceived skill development, and leadership confidence. Graduate level students help in training sessions, data collection and implementation of intervention.

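### Aim 2 plans no baseline-adjusted MT+ minus MT difference with a confidence interval at 3 and 6 months, although the pilot is meant to supply effect sizes for the next trial

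*Combined protocol and SAP*

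**What the plan says.** The Accrual section fixes the primary test: "A within-between interaction will be the primary test of significance (time*group interaction". With two arms and three time points this is a test on 2 degrees of freedom. The same section states what the pilot is for: "It is important for this study that we obtain reliable estimates of effect size with which to perform a power analysis for subsequent research".

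Statistical Analysis, Aim #2, applies repeated-measures ANOVA to weight, diet and physical activity. It justifies these models "as they provide a direct measure of differences between the intervention and comparison groups in weight loss and dietary and PA behaviors" and adds "as well as effect size estimates", without naming the measure, the visit or an interval. If attrition is higher than expected, "a maximum likelihood estimation method (e.g. mixed models) will be used instead of RM-ANOVA". For weight there is one more analysis: "Overall weight lost at follow-up will be assessed via an independent groups t-test". Aim 2 describes 6 months as the follow-up, so this is in effect a comparison of 6-month change. Whether it is in kg or percent is not stated. Outcomes that are not normally distributed are to be transformed or analysed nonparametrically.

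The descriptive plan reads: "Means and standard deviations will be calculated for all continuous variables and measures at each time point". The Methods place baseline measurement before allocation: "Following informed consent and completion of baseline visit, eligible participants will be randomized 1:1 to either intervention or comparison group". The Summary makes weight loss primary in both kg and percent of body weight.

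**The concern.** Aim 2 asks about 3 and 6 months, and the pilot is to hand effect sizes to a larger trial. That trial will need a signed arm difference at a named visit, with its uncertainty. The analysis text does not commit to one, except indirectly for weight at 6 months through the t-test. For weight at month 3, and for diet and physical activity at either visit, it names no arm contrast.

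The baseline value of each outcome is already collected and is unaffected by allocation. Using it as a covariate normally tightens the arm comparison at almost no cost, and the plan does not do so. Nor does it say how percent weight change, one of the two primary scales, is to be analysed.

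At stake are the usefulness and precision of the estimates passed on, not the validity of the tests.

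**Working it through.** **Inputs.** From the Accrual section: f = .10, alpha .05, three time points, correlation rho = .5, 164 men for 80% power, 80 men planned, up to 30% attrition (80 × 0.7 = 56 completers). The documents give no SD and no correlation for any single outcome, so results are in SD units. Equal SDs at all visits, one common correlation and equal arms are assumed.

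**1. The plan's own figure.** Noncentral F with lambda = N × 3 × f² / (1 − rho), on 2 and 2(N − 2) degrees of freedom.

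- N = 164: lambda = 164 × 3 × .01 / .5 = 9.84, power 0.805. N = 162 gives 0.7998, so 164 reproduces.
- N = 80: lambda = 4.80, power 0.479.
- N = 56: lambda = 3.36, power 0.347.

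At the assumed effect the F-test is more likely than not to be non-significant. The plan accepts this for a pilot, which makes the estimate and its interval the main product.

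**2. What f = .10 says about month 6.** Let the arm difference at baseline, month 3 and month 6 follow a pattern scaled by d. The interaction SD is the root mean square of half the deviations of these differences from their mean. Setting it to .10 gives d.

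| Pattern | Interaction SD | d | 6-month difference | Total N, later 6-month change-score t-test, 80% power |
|---|---|---|---|---|
| Linear (0, d/2, d) | 0.204d | 0.490 | 0.49 SD | 134 |
| Early and held (0, d, d) | 0.236d | 0.424 | 0.42 SD | 178 |
| Month 6 only (0, 0, d) | 0.236d | 0.424 | 0.42 SD | 178 |
| Half lost by month 6 (0, d, d/2) | 0.204d | 0.490 | 0.24 SD | 526 |
| Month 3 only (0, d, 0) | 0.236d | 0.424 | 0 | none suffices |

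For a given 6-month difference the interaction SD is smallest when month 3 lies halfway, so 0.49 SD is the largest size that f = .10 allows. The sign is also lost, because f is built from squares.

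**3. Precision at one visit.** The variance is 2(1 − rho) for a change score and 1 − rho² after baseline adjustment. Half-width = t(.975) × √(4 × variance / N), with N − 2 and N − 3 degrees of freedom respectively.

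At rho = .5 and N = 80:

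- change score: 1.991 × √(4 × 1 / 80) = 0.445
- adjusted: 1.991 × √(4 × 0.75 / 80) = 0.386
- saving: 1 − 0.386/0.445, about 13%

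At N = 56 the half-widths are 0.536 and 0.464, again about 13%.

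| rho | Change score, N = 80 | Adjusted, N = 80 | Saving |
|---|---|---|---|
| .5 | 0.445 | 0.386 | 13.4% |
| .7 | 0.345 | 0.318 | 7.8% |
| .8 | 0.282 | 0.267 | 5.1% |
| .9 | 0.199 | 0.194 | 2.5% |
| .95 | 0.141 | 0.139 | 1.2% |

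**4. Percent weight change.** It is 0 for every man at baseline. Entered as (0, month 3, month 6), it still gives a working time-by-group test. Simulation with 80 men gave a type I error near .05. For a constant benefit of 0.5 SD of percent change, power was .63, against .59 for the 6-month t-test.

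**The case against.** The strongest reply is that weight, the primary outcome, is already served at 6 months. The t-test on weight lost compares arms on change from baseline. It yields a signed difference and the SD needed to size a later trial, and an interval follows from the same output. This stands. The ambiguity in step 2 therefore bites mainly on diet and physical activity, and on the shape of the weight effect over time. The planned means at each visit include baseline, so differences in change can also be formed for every outcome. What those summaries lack is the standard error of the change.

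The second reply is that the precision gain is smallest where it matters most. Body weight in kg may correlate at .90 to .95 over six months (an assumption), and the saving is then 1.2% to 2.5%. No gain from the covariate is shown for percent weight change. This stands too, and it makes the missing intervals and month-3 contrast the stronger argument for weight.

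Third, extra contrasts on several outcomes raise multiplicity, and a mean difference does not sit directly with the rule for non-normal outcomes. Both are fair and are met in the fix.

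A reader might infer that the interaction would miss a constant benefit on percent weight. That would require an analysis of months 3 and 6 alone, which the plan does not propose. With the planned three time points the benefit is detected (step 4). A reader might also infer that a single adjusted contrast should replace the interaction as primary. At rho = .5 with 80 men, the adjusted average of the two visits has power 0.755 for an early, held effect, against 0.479 for the interaction. It has only 0.263 if the effect is at one visit, so neither dominates.

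**Conclusion.** The point holds as a loss of efficiency and a reporting gap. Aim 2 names no baseline covariate, no confidence interval, no month-3 arm contrast and no visit-specific contrast for diet or physical activity, although the pilot is meant to deliver usable effect sizes. The documents do not support reading this as an invalid analysis: both planned tests are sound.

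At the plan's rho = .5, an interaction effect size of .10 is compatible with a 6-month difference from 0 to 0.49 SD, and baseline adjustment narrows the interval by about 13% against the change score. The saving shrinks to 2.5% at rho = .9 and 1.2% at .95. These figures assume equal SDs and a common correlation across visits. The absence of named contrasts and intervals does not depend on them. For percent weight change, what is missing is a statement of how the arms are compared. The point ranks between minor and something the sponsor should change.

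**What to change.** Keep the time-by-group interaction as the primary test. For each outcome, add one longitudinal model of the 3- and 6-month values on arm, visit, arm × visit, the outcome's own baseline and baseline × visit, or a constrained longitudinal model. Report the adjusted MT+ minus MT difference with a 95% interval at 3 and at 6 months for weight, diet and physical activity. Label these as estimation without multiplicity control. Where the non-normality rule leads to a transformation, report on the transformed scale. State that percent weight change is compared between arms at each visit.

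What happens to the t-test depends on timing. The document is dated 05-27-2022, and the section on retaining Lose-It accounts, which reports a consultation on 1-14-19, already refers to men past their 6-month visit. The SAP should state whether outcomes had been seen by arm. If they had not, the adjusted 6-month weight difference can replace the unadjusted t-test. If they had, keep the t-test, add its interval, and label the adjusted model supportive.

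The cost is SAP wording, one extra model per outcome and one degree of freedom per visit contrast. No new data are needed, and mixed models are already the plan's fallback for high attrition.
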